## 6 Statistical Considerations

The following section describes the statistical methods for the clinical investigation and justification of the design.

### 6.1 Hypotheses

#### 6.1.1 Primary Endpoint Hypothesis

The primary endpoint is intended to demonstrate non-inferiority of the qualification rate at the end of the initial trial evaluation period for Group 1 (AB) compared to Group 2 (TB).

For each randomization group, the qualification rate is defined as the number of subjects who are identified as "qualified for permanent system implant" divided by total subjects who complete the initial trial evaluation period for the respective randomized group.

Qualification for permanent system implant is defined by a composite in which a subject meets all of the following conditions:

- >50% patient reported pain relief (PRP) at the end of the trial evaluation period
- Trial evaluation period lasted for a minimum of 3 days
- Physician recommends subject for permanent system implant
- Subject reports a willingness to pursue a permanent system implant
- 

Subjects are not qualified for permanent system implant if they meet both of the following:

- ≤50% PRP at the end of the trial evaluation
- Trial evaluation period lasted for a minimum of 5 days

Hypothesis:

The hypothesis is formally addressed as:

$$H_0: P_{AB} - P_{TB} \leq -15\%$$

[figure not shown]
$$H_1: P_{AB} - P_{TB} > -15\%$$

where

[figure not shown]
$P_{AB}$  = permanent system qualification rate of Group 1 (AB)

$P_{TB}$  = permanent system qualification rate of Group 2 (TB)

#### 6.1.1.1 Analysis Methodology

#### 6.1.1.2 Sample Size Determination

#### 6.1.1.3 Analysis Populations

The analysis population includes subjects who are randomized and either qualify for a permanent system implant or do not qualify for a permanent system implant, as defined earlier.

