### 4.3.1 Primary Endpoint

The primary endpoint is the qualification rate for permanent system implant at the end of the initial trial evaluation period.

Qualification for permanent system implant is defined by a composite in which a subject meets all of the following conditions:

- >50% patient reported pain relief (PRP) at the end of the trial evaluation
- Trial evaluation period lasted for a minimum of 3 days
- Physician recommends subject for permanent system implant
- Subject reports a willingness to pursue a permanent system implant

Subjects are not qualified for permanent system implant if they meet **both** of the following:

- ≤50% PRP (patient reported pain relief) at the end of the trial evaluation
- Trial evaluation period lasted for a minimum of 5 days

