## **5.11 Study Committees**

### **5.11.1 Steering Committee (SC)**

A Steering Committee will advise the Sponsor on key aspects related to the development, execution, analysis and reporting, and overall conduct of the clinical investigation. A Steering Committee charter will define membership of the committee and outline the purpose, roles, responsibilities, and general rules of operation for the Steering Committee. This charter is maintained by the Sponsor and sets forth the procedures for the implementation of the Steering Committee.

A Medical Monitor will be utilized for this study. The Medical Monitor is responsible for reviewing each subject's lead placement imaging to determine if the lead placement guidelines were followed. Once the investigator completes the trial implant procedure, the images and applicable source documentation will be provided to the Medical Monitor for evaluation. If the Medical Monitor determines that the patient was implanted outside the required guidelines, a protocol deviation will be issued and the patient will be excluded from the primary endpoint analysis.

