#### 6.1.1.5 Missing Data

A sensitivity analysis will be carried in the same manner as the primary analysis, except the subjects who were randomized, underwent the trial system implant and did not complete the initial trial period will be included in the analysis and be treated as non-qualified subjects.

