The primary marker of success during the typical SCS trial evaluation period is qualification for permanent implant. Qualification per standard of care for SCS devices includes a successful trial evaluation period defined by subject's assessment of 50% or more pain relief during the trial evaluation, physician's recommendation, and the subject's willingness to continue to the permanent system. As such, the current clinical investigation defines qualification for permanent implant as a composite endpoint based upon standard of care to be used as for the primary endpoint. Demonstration of non-inferiority will establish that the anatomic placement technique is similar to traditional, targeted techniques in terms of subject selection for permanent implant. Secondary and descriptive endpoints will provide evidence of the physician and patient experience with both types of implant procedures and with the Invisible Trial System, overall.

As the primary hypothesis will be tested prior to actual permanent implant status, the clinical investigation will end at the qualification stage without consideration of the actual permanent implant status for subjects. Qualification based on efficacy, subject self-selection, and physician discretion is sufficient to make inferences about the anatomic procedure and Invisible Trial System features.

Failure to qualify for this study is contingent upon a minimum of 5 days of stimulation. Anecdotal reports indicated that burst stimulation may take up to 5 days to impart full benefit; whereas, tonic stimulation does not historically have a wash-in period to reach full benefit. As such, failures occurring before 5 days may be a product of insufficient exposure to burst therapy, and the primary endpoint is contingent upon equitable treatment between randomization arms in all other aspects excepting procedure. Additionally, subjects who fail the burst trial and proceed to an extended trial evaluation with tonic stimulation will need to ensure that they are provided sufficient time to assess the alternate stimulation mode. At present, the wash-out period for burst, if any, has not been established but is suspected to be at least a few hours and up to 2 days. As such, subject's ending their trial evaluation before 5 days without meeting criteria for qualification for permanent implant will be considered a deviation and treated as missing data. Use of this criterion will also

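### Sections 6.1.1 and 6.1.1.3, as worded, give different primary denominators: a completer at 5 days or more with over 50% relief but no recommendation or no willingness is a failure under one and excluded under the other

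*Combined protocol and SAP*

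**What the plan says.** Sections 4.3.1 and 6.1.1 define two classes. A subject is qualified if all four conditions hold: patient-reported pain relief (PRP) above 50%, a trial period of at least 3 days, "Physician recommends subject for permanent system implant", and the subject is willing to go on to a permanent system. The other class has its own definition: "Subjects are not qualified for permanent system implant if they meet both of the following", namely PRP of 50% or less and a period of at least 5 days.

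Section 6.1.1 takes the number qualified "divided by total subjects who complete the initial trial evaluation period for the respective randomized group". Section 6.1.1.3 describes the analysis population as "subjects who are randomized and either qualify for a permanent system implant or do not qualify for a permanent system implant, as defined earlier".

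Three other passages affect who is counted:

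- Section 6.2 says "Failure to qualify for this study is contingent upon a minimum of 5 days of stimulation". It adds that subjects who end "before 5 days without meeting criteria for qualification for permanent implant will be considered a deviation and treated as missing data".
- The sensitivity analysis in 6.1.1.5 adds subjects who were randomized and implanted but "did not complete the initial trial period will be included in the analysis and be treated as non-qualified subjects".
- Section 5.11.1 says that if the Medical Monitor finds a subject "implanted outside the required guidelines, a protocol deviation will be issued and the patient will be excluded from the primary endpoint analysis".

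Sections 6.1.1.1, 6.1.1.2 and 6.4 show headings without text in the public document. That is not held against the plan, but it means they cannot settle the question.

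**The concern.** A subject can finish 5 days or more, report over 50% relief, and still not be recommended or not want the implant. That subject meets neither definition. Under the 6.1.1 formula the subject completed and did not qualify, so counts as a failure. Under 6.1.1.3 taken at its word, the subject is in neither class and drops out. The sensitivity analysis does not bring the subject back, because it adds only people who did not complete.

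Under the literal reading, among subjects with PRP above 50%, a withheld recommendation or a refusal removes the subject and never scores as a failure. Both are post-randomization judgments, and the recommendation may come from a physician who knows the allocation, since 5.4.2 says implanting physicians cannot be blinded. This is the only primary endpoint, and under 6.7 study success rests on it. If the removed share or the pain relief differs by arm, the non-inferiority result can move in either direction.

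**Working it through.** **Step 1: which subjects are treated differently.** At 5 days or more, the classes are:

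| PRP | Recommended and willing? | 6.1.1 formula | Literal 6.1.1.3 |
|---|---|---|---|
| >50% | both | qualified | qualified |
| >50% | one or both missing (3 of 4 combinations) | failure | excluded |
| ≤50% | any (4 combinations) | failure | not qualified |

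At 5 days or more, the discrepancy is confined to the middle row.

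On days 3–4, subjects who do not qualify may also have completed in the sense of 6.1.1, because 5.4.4 sets a 3-day minimum. Section 6.2 makes them missing, and the literal 6.1.1.3 already leaves them out. For them, only the word *complete* in the 6.1.1 formula is loose.

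**Step 2: formulas.** The plan shows no sample size, alpha, power or expected rate, so there is no figure to reproduce. Let r be the share of completers with PRP >50%, and x (the gap) the share of those not recommended or unwilling, all at 5 days or more.

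- Rate under 6.1.1: r(1 − x).
- Rate under literal 6.1.1.3: r(1 − x)/(1 − r·x).

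The −15 point margin (6.1.1) and 1:1 allocation (4.1) come from the document. **Everything else is assumed:** 160 completers per arm, r = 0.70 in both arms, an unpooled Wald lower bound, one-sided 2.5%.

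Worked case, gap 10% in AB (anatomic) and 5% in TB (targeted):

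- 6.1.1: 0.70 × 0.90 = 63.0% and 0.70 × 0.95 = 66.5%, difference −3.5 points.
- Literal 6.1.1.3: 0.630/(1 − 0.070) = 67.7% and 0.665/(1 − 0.035) = 68.9%, difference −1.2 points.

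**Step 3: chance of declaring non-inferiority** (binomial enumeration; number analysed under 6.1.1.3 treated as random):

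| Gap AB / TB | Difference, 6.1.1 | Difference, 6.1.1.3 | Chance, 6.1.1 | Chance, 6.1.1.3 |
|---|---|---|---|---|
| 10% / 5% | −3.5 | −1.2 | 58% | 74% |
| 5% / 3% | −1.4 | −0.4 | 74% | 79% |
| 5% / 10% | +3.5 | +1.2 | 94% | 86% |
| 5% / 5% | 0 | 0 | 81% | 81% |
| 10% / 10% | 0 | 0 | 79.6% | 79.2% |

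The first row becomes 40% and 54% with 100 completers per arm, and 72% and 86% with 220.

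**Step 4: true completer difference exactly −15.** Keep r_TB = 0.70 and set r_AB = (0.70(1 − x_TB) − 0.15)/(1 − x_AB). False non-inferiority under 6.1.1 is about 2.4% throughout.

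| Gap AB / TB | True difference under 6.1.1.3 | False non-inferiority under 6.1.1.3 |
|---|---|---|
| 10% / 5% | −14.3 | 3.3% |
| 5% / 3% | −14.9 | 2.5% |
| 5% / 5% | −16.0 | 1.6% |
| 10% / 10% | −17.0 | 1.0% |
| 5% / 10% | −18.5 | 0.5% |

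**Step 5: one dataset, two answers.** This example is constructed to lie near the margin. PRP >50% in 108 of 160 AB and 112 of 160 TB, of whom 11 and 6 are not recommended or unwilling.

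- 6.1.1: 97/160 = 60.6% and 106/160 = 66.3%; difference −5.6, standard error 5.38, lower limit −5.6 − 1.96 × 5.38 = −16.2. Not met.
- Literal 6.1.1.3: 97/149 = 65.1% and 106/154 = 68.8%; difference −3.7, standard error 5.40, lower limit −3.7 − 1.96 × 5.40 = −14.3. Met.

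**The case against.** The strongest reply is that the plan already means these subjects to be failures. Section 6.1.1 says subjects are not qualified if both conditions hold; it does not say only if. Sections 4.1 and 5.4.4 and descriptive endpoint 5 use not qualifying in its ordinary sense. Section 6.2 makes missing only those who end before 5 days, which implies that a later non-qualifier is counted. The rate formula itself names all completers. This stands as evidence of intent. It does not close the gap: 6.1.1.3 points back to an explicit two-condition definition, and a plain complement would turn non-qualifiers before day 5 into failures, contrary to 6.2. The benign reading needs a combined rule that neither 6.1.1 nor 6.1.1.3 states.

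It is also fair to say that every effect size here is assumed, that no figure in the documents suggests a large or unequal gap, and that descriptive endpoint 4 would show each criterion by arm. All of that stands and limits the severity. Endpoint 4 would reveal an imbalance, but would not say which denominator governs the test.

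Four stronger readings are tempting, and the documents do not support them:

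- *Refusals and withheld recommendations never count as failures.* With PRP of 50% or less and at least 5 days, the subject is a failure either way.
- *The 5-day rule is absent from 6.1.1.* It is part of the not-qualified definition there.
- *The literal population generally inflates false non-inferiority.* In the five cases tried, one was materially higher, one about the same and three lower.
- *The sponsor will in fact drop these subjects.* The methodology section is not visible, and failure is the likelier intent.

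**Conclusion.** Wrong as written, and it should be fixed. Confidence is high that the visible wording of 6.1.1 and 6.1.1.3 conflicts for completers at 5 days or more with PRP >50% and no recommendation or no willingness. Confidence is moderate on the consequence, because the documents do not give the frequency of such subjects or any difference between arms.

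Under the stated assumptions, the choice of denominator moves the chance of declaring non-inferiority by up to 16 points at 160 completers per arm (58% to 74%). It can also lower it (94% to 86%), and it makes almost no difference when gap and pain relief are equal in both arms. At a true difference of −15, false non-inferiority under the literal population ranges from 0.5% to 3.3%, against about 2.4% under 6.1.1. An equal gap with unequal relief also shifts the estimate, as the −16.0 and −17.0 rows show.

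Two loose ends belong with this point: the word *complete* in 6.1.1 may take in subjects whom 6.2 calls missing, and the 5.11.1 exclusion appears in neither 6.1.1 nor 6.1.1.3.

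**What to change.** Use one set as both rate denominator and analysis population, and state it in 6.1.1 and 6.1.1.3:

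1. As an analysis definition only, a subject with at least 5 days who does not meet the full composite is non-qualified and stays in the denominator. This includes PRP >50% without recommendation or without willingness.
2. Align *complete* in 6.1.1 with 6.2: subjects who end before 5 days without qualifying are missing and outside the primary denominator. Say in 6.1.1.5 whether the sensitivity analysis includes them.
3. Cross-reference the 5.11.1 exclusion in both sections, so that a single set results.
4. Add a cross-reference in 4.3.1 to this analysis definition, so that its two-part list does not conflict. Leave the clinical criteria for the extended period unchanged.

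The cost is a few sentences, settled before the data are analysed. All components of the composite are already collected. The downside is that reported rates will be lower than under the literal 6.1.1.3: with PRP >50% in 70%, for example, 66.5% instead of 68.9% at an assumed 5% gap, or 63.0% instead of 67.7% at 10%.

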#### 6.1.1.4 Subgroup Analysis

The primary endpoint will be reported separately for female and male subjects.

#### 6.1.1.5 Missing Data

A sensitivity analysis will be carried in the same manner as the primary analysis, except the subjects who were randomized, underwent the trial system implant and did not complete the initial trial period will be included in the analysis and be treated as non-qualified subjects.

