## 4 Clinical Investigation Design

### 4.1 Clinical Investigation Design

This is a randomized, controlled, single blind, multi-center clinical investigation comparing success rates for anatomically placed leads to conventional, targeted lead placement for BurstDR™ during the trial evaluation period with the SJM™ Invisible Trial System. Subjects will be blinded to treatment group and randomized in a 1:1 ratio as follows:

- Group 1 (AB): anatomic lead placement followed by BurstDR™ stimulation during an initial trial evaluation period
- Group 2 (TB): targeted lead placement followed by BurstDR™ stimulation during an initial trial evaluation period

If the subject qualifies for permanent system implant as defined in section 4.3.1 after the initial trial evaluation period, the subject will exit the clinical investigation and continue their treatment per the physician's standard of care. Subjects who do not qualify for permanent system implant as defined in section 4.3.1 after the initial trial evaluation period may participate in an extended trial evaluation period, per physician discretion, during which they will be programmed with tonic stimulation. Subjects continuing to an extended trial evaluation period will be followed through the completion of the extended trial period. At the end of the extended trial evaluation period, subjects will exit the clinical investigation.

The randomization diagram (Figure 3) and the study flow chart (Figure 4) are shown below.

Figure 3: Randomization Diagram

[figure not shown]
[figure not shown]

Figure 4: Study Flow Chart

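### The only visible missing-data sensitivity analysis scores non-completers as failures in both arms, so how hard it tests the non-inferiority result depends on how non-completion splits between the arms

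*Combined protocol and SAP*

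**What the plan says.** Section 6.1.1 (Primary Endpoint Hypothesis) tests whether the AB qualification rate minus the TB rate exceeds -15 points. Each rate is the number of qualified subjects "divided by total subjects who complete the initial trial evaluation period". Section 6.1.1.3 limits the analysis population to "subjects who are randomized and either qualify for a permanent system implant or do not qualify for a permanent system implant". Section 6.2 adds that a subject who stops before 5 days without qualifying "will be considered a deviation and treated as missing data".

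Section 6.1.1.5 (Missing Data) then gives one further analysis: "A sensitivity analysis will be carried in the same manner as the primary analysis", except that randomized and implanted subjects who "did not complete the initial trial period will be included in the analysis and be treated as non-qualified subjects". The rule is the same for both arms, and no other margin is stated.

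Three other places bear on this:
- Section 5.10 lists reasons for withdrawal that include an unsuccessful trial implant with ineffective stimulation, lead revision and system explant.
- Section 5.4.2 lets randomization take place at the end of the baseline visit or just before surgery.
- Section 6.7 makes trial success depend on the primary endpoint alone.

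The bodies of 6.1.1.1 (Analysis Methodology) and 6.1.1.2 (Sample Size Determination) do not appear in the public text.

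**The concern.** Scoring missing subjects as failures is often thought of as the cautious choice. In a non-inferiority comparison of two proportions it need not be. If the same share of each arm is set to failure, both rates shrink by the same factor, and so does the gap between them, while the margin stays at -15 points. An analysis meant to challenge the completers-only result can then be the easier one to pass, and its agreement with that result would be partly built in.

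Non-completion is likely to matter here. The protocol withdraws subjects for lead revision and treats early stoppers as missing, and such events could differ by placement technique. The primary analysis drops these subjects, so the analysis in 6.1.1.5 is the only visible check on what dropping them does. Subjects randomized but never implanted enter neither visible analysis.

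**Working it through.** The public text shows no sample size, alpha, power or dropout rate, so there is no figure of the plan's own to reproduce. What follows is an illustration.

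**Inputs from the documents**
- Margin: -15 points (6.1.1).
- Allocation: 1:1 (4.1).
- Scoring rule for non-completers (6.1.1.5).
- Trial-to-implant rates of 41% to 71% or more (section 2). This is background literature and not a stated design value; both ends are used as assumed TB rates.

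**Assumptions:** one-sided alpha 2.5%; 80% power at a true difference of zero; non-completion of 5%, 10% or 20%; a true difference of -15 points; non-completers who would have qualified as often as completers.

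**Step 1. Effect on the difference.** Let dA and dT be the non-completion shares and pA and pT the completer rates. Scoring non-completers as failures gives

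(1 - dA) pA - (1 - dT) pT = (pA - pT) + (dT pT - dA pA).

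The change favours AB when dA/dT is below pT/pA and counts against AB when it is above. At the margin this break-even ratio is 0.71/0.56 = 1.27 (TB 71%) or 0.41/0.26 = 1.58 (TB 41%).

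**Step 2. Equal non-completion d.** The difference becomes (1 - d) × (-15): -14.25 points at 5%, -13.5 at 10% and -12.0 at 20%.

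**Step 3. Sizes.** Completers per arm: n = (1.96 + 0.84)² × 2p(1 - p) / 0.15², which gives 144 at 71% and 169 at 41%. Implanted per arm: N = n/(1 - d), rounded up.

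**Step 4. Probability that this analysis shows non-inferiority.** Φ((diff + 0.15)/SE - 1.96), with unpooled SE.

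Example, TB 71%, d = 10%, N = 160. The rates become 0.639 and 0.504. SE = √[(0.639 × 0.361 + 0.504 × 0.496)/160] = 0.0548. Then Φ(0.015/0.0548 - 1.96) = Φ(-1.69) = 4.6%.

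| Non-completion, each arm | TB 71% | TB 41% |
|---|---|---|
| 5% | 3.4% | 3.5% |
| 10% | 4.6% | 5.1% |
| 20% | 8.3% | 10.5% |

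A simulation with 400,000 runs per setting gave 4.3% and 8.2% (TB 71%) and 5.0% and 10.5% (TB 41%) at 10% and 20%. Completers-only stayed near 2.5%.

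**Step 5. Unequal non-completion** (N = 160 for TB 71%, 188 for TB 41%)

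| AB / TB non-completion | Difference, TB 71% | False non-inferiority | Difference, TB 41% | False non-inferiority |
|---|---|---|---|---|
| 20% / 10% | -19.1 | 0.3% | -16.1 | 1.4% |
| 5% / 15% | -7.2 | 29.5% | -10.2 | 17.7% |

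The same rule is stricter than the completers-only analysis in the first row and far looser in the second.

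**Step 6. The opposite extreme.** With AB missing scored non-qualified, TB missing scored qualified and 10% missing per arm, a completer difference of -15 becomes 0.9 × (-15) - 10 = -23.5 points. False non-inferiority falls to 0.01-0.02%, but with truly equal rates only about 16% of trials would pass. It is a bound, not a sensible single test.

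**The case against.** **Failure is the real outcome for many non-completers.** This stands. A subject withdrawn for ineffective stimulation or lead revision can fairly be called non-qualified, and the smaller difference is then not bias. Suppose 70% of non-completers are genuine failures and the true difference over all implanted subjects is -15 points. The scored difference is -15 × (1 - d)/(1 - 0.7d), that is -14.5 points at 10% and -14.0 at 20%. With the sizes in step 3, false non-inferiority is 3.1-3.2% and 4.0-4.2%. A reader might infer that the failure rule itself is wrong; the withdrawal reasons in 5.10 do not support that.

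**The direction is not fixed.** This stands too. A reader might infer that the rule always helps AB. Steps 1 and 5 show that it does not: if anatomic placement does worse by causing more withdrawals, the rule counts against AB.

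**These are not the trial's error rates.** Correct. A reader might infer that the plan inflates its type I error. Under 6.7 success rests on the primary endpoint alone. In the simulation with equal non-completion, both analyses passed together in 2.0-2.5% of trials. The harm is weak reassurance, not more false claims of success.

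**Other analyses may exist.** Possible. The body of 6.1.1.1 is missing from the public version, so a reader should not infer that the full plan has no other check. The section headed Missing Data is present, however, and names only one.

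**The never-implanted group may be small**, since randomization can be done just before surgery. No count is given either way.

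None of this supplies a visible analysis in which the assumption about missing subjects differs by arm.

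**Conclusion.** The point holds in a limited form. The only visible missing-data sensitivity analysis is anti-conservative for non-inferiority when non-completion is similar in the two arms or higher in TB. It turns stricter when the AB/TB ratio of non-completion exceeds about 1.3 to 1.6 at the margin. How hard it tests the result therefore depends on a dropout pattern that is unknown in advance, and agreement with the primary result cannot by itself be called robustness.

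The shrinkage by (1 - d) is algebra. The error rates in step 4 rest on the assumed alpha, power, TB rates and non-completion, and on non-completers resembling completers. At 5% non-completion the effect is modest, and the initial evaluation has a minimum of only 3 to 5 days, so low non-completion is possible. This is a worthwhile improvement to a supportive analysis and not a flaw in the primary test.

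**What to change.** Keep the analysis in 6.1.1.5 and add a tipping-point analysis by arm over all randomized subjects:

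- Keep documented treatment failures, such as ineffective stimulation or lead revision, as non-qualified in both arms.
- For the other missing subjects, including those never implanted, vary the assumed qualification rate separately in AB and TB.
- Mark one point on the grid as delta-adjusted imputation under the null: missing TB at the observed TB rate, missing AB at that rate minus 15 points. Show AB non-qualified with TB qualified as the extreme.
- Report where the non-inferiority conclusion changes, together with non-completion counts and reasons by arm.
- State how implants that the Medical Monitor excludes from the primary analysis (5.11.1) enter, since 6.1.1.5 does not mention them.

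The delta-adjusted point should not be the sole test of robustness. In simulation at TB 71% its error was 0.8-1.5%, below the nominal 2.5%, so a result could miss that point and still be reasonably secure.

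The cost is some added SAP wording and a few lines of code on data already collected. The downside is that the reported robustness may look less favourable.
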